15.2 Recording of an Adverse Event

During Phase Ib, all adverse events will be entered into OnCore[®], whether or not the event is believed to be associated with use of the study drug. During Phase II, all grade 3 and above adverse events will be entered into OnCore[®], whether or not the event is believed to be associated with use of the study drug. Data about these events and their severity will be recorded using the NCI CTCAE v4.0.

The Investigator will assign attribution of the possible association of the event with use of the investigational drug, and this information will be entered into OnCore[®] using the classification system listed below:

Relationship	Attribution	Description
Unrelated to investigational drug/intervention	Unrelated	The AE is clearly NOT related to the intervention
	Unlikely	The AE is doubtfully related to the intervention
Related to investigational drug/intervention	Possible	The AE may be related to the intervention
	Probable	The AE is likely related to the intervention
	Definite	The AE is clearly related to the intervention

Signs or symptoms reported as adverse events will be graded and recorded by the Investigator according to the CTCAE. When specific adverse events are not listed in the CTCAE they will be graded by the Investigator as *none, mild, moderate* or *severe* according to the following grades and definitions:

- Grade 0 No AE (or within normal limits)
- Grade 1 Mild; asymptomatic or mild symptoms; clinical or diagnostic observations only; intervention not indicated
- Grade 2 Moderate; minimal, local, or noninvasive intervention (e.g., packing, cautery) indicated; limiting age-appropriate instrumental activities of daily living (ADL)
- Grade 3: Severe or medically significant but not immediately life-threatening; hospitalization or prolongation of hospitalization indicated; disabling; limiting self-care ADL
- Grade 4: Life-threatening consequences; urgent intervention indicated
- Grade 5: Death related to AE

15.3 Follow-up of Adverse Events

Reportable SAEs are those that occur after the first dose of PLX3397 and until 21 days after the last dose of combined therapy. All adverse events will be followed with appropriate medical management until resolved. Patients removed from study for unacceptable adverse events will be followed until resolution or stabilization of the adverse event. For selected adverse events for which administration of the investigational drug was stopped, a re-challenge of the subject with the investigational drug may be conducted if considered both safe and ethical by the Investigator.

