3.2 Inclusion Criteria

- Pathologically confirmed diagnosis of breast cancer with documented progressive disease.
- Patients with stable brain metastases are eligible for this trial. Stable brain metastases defined as stable disease for one month and not on active treatment including steroids.
- Concomitant therapy with bisphosphonates is allowed.
- Stable dose coumadin anticoagulation is allowed, providing that anticoagulation can be safely held to an INR within normal range for the purpose of tumor biopsy. LMWH is the preferred method of anticoagulation.
- PT/INR and PTT \leq Grade 1 within two weeks before initial biopsy of visceral organs.
- Measurable disease, as defined by RECIST v1.1 guidelines or evaluable disease. Bone metastases must be evaluable.
- Disease amenable to core biopsy. Patients with pulmonary metastases as their only site of disease may enroll on this trial and will not undergo biopsy.
- For Phase Ib: patients with HER2 overexpressing disease must have been previously treated with trastuzumab (patients with HER2 overexpressing disease are not eligible for the Phase II trial).
- Age eighteen years or older.
- ECOG performance status ≤ 2 .
- Life expectancy of ≥ 12 weeks.
- Patients with \leq Grade 1 peripheral neuropathy are eligible for this trial using the CTCAE v4.0, regardless of use of therapy for neuropathy including gabapentin.
- Adequate bone marrow reserve: ANC ≥ 1000 , platelets $\geq 100,000$.
- Adequate renal function: serum creatinine $\leq 1.5x$ upper limit of normal OR calculated creatinine clearance ≥ 50 ml/min.
- Sodium and potassium levels \leq Grade 1.
- Adequate hepatic function: AST and ALT ≤ 2.5 x ULN, and total bilirubin $\leq 1.5x$ upper limit of normal. In patients with liver dysfunction due to hepatic metastases, AST and ALT are permitted to be ≤ 5 times the ULN. No clinical evidence of heart failure or history of untreated ejection fraction below the lower limit of normal per institutional standards, or significant QT prolongation ($>$ Grade 1, 480 msec) no history of congenital long QT syndrome, and no use of drugs known to increase the risk of Torsades de Point - patients may be eligible for study if the drug can be changed to another agent with less risk.
- Able to take oral medications and maintain hydration.

- Ability to give written informed consent and willingness to comply with the requirements of the protocol.

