9.0 Criteria for Evaluation

9.1 Response Definitions

Evaluable for toxicity: All patients will be evaluable for toxicity from the time of their first treatment with PLX3397

Evaluable for objective response: Only those patients who have measurable disease present at baseline, have received at least one cycle of therapy, and have had their disease re-evaluated will be considered evaluable for response. These patients will have their response classified according to the definitions stated below. (Note: Patients who exhibit objective disease progression prior to the end of cycle 1 will also be considered evaluable.)

Evaluable Non-Target Disease Response: Patients who have lesions present at baseline that are evaluable but do not meet the definitions of measurable disease, have received at least one cycle of therapy, and have had their disease re-evaluated will be considered evaluable for non-target disease. The response assessment is based on the presence, absence, or unequivocal progression of the lesions.

Disease Parameters

Measurable disease: Measurable lesions are defined as those that can be accurately measured in at least one dimension (longest diameter to be recorded) as ≥ 20 mm (≥ 2 cm) by chest x-ray or as ≥ 10 mm (≥ 1 cm) with CT scan, MRI, or calipers by clinical exam. All tumor measurements must be recorded in millimeters (or decimal fractions of centimeters).

Malignant lymph nodes: To be considered pathologically enlarged and measurable, a lymph

node must be ≥ 15 mm (≥ 1.5 cm) in short axis when assessed by CT scan (CT scan slice thickness recommended to be no greater than 5 mm [0.5 cm]). At baseline and in follow-up, only the short axis will be measured and followed.

Non-measurable disease: All other lesions (or sites of disease), including small lesions (longest diameter < 10 mm [< 1 cm] or pathological lymph nodes with ≥ 10 to < 15 mm [≥ 1 to < 1.5 cm] short axis), are considered non-measurable disease. Bone lesions, leptomeningeal disease, ascites, pleural/pericardial effusions, lymphangitis cutis/pulmonitis, inflammatory breast disease, and abdominal masses (not followed by CT or MRI), are considered as non-measurable.

Note: Cystic lesions that meet the criteria for radiographically defined simple cysts should not be considered as malignant lesions (neither measurable nor non-measurable) since they are, by definition, simple cysts.

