14.0 Correlative studies

14.1 Tumor biopsies

Tumor biopsies will be obtained from accessible tumor tissue following the guidelines provided below before treatment start in all eligible patients. Patients enrolled on the Phase II trial will be asked to have a second core biopsy or FNA, depending on ease and site of biopsy. Patients who refuse the second biopsy will be allowed to stay on study treatment. Every attempt will be made to obtain tumor tissue at the time of a clinical procedure, if possible. Patients with lung only metastases will not be required to have biopsies, but will be allowed to enroll on this trial.

Core biopsies of the breast will be performed by a qualified radiologist or surgeon, according to institutional guidelines for a diagnostic biopsy. Biopsies of other sites may be done by radiology, pathology or qualified surgeons. When required, radiographic coordination will be arranged. Tissue specimens will be collected from recurrent or metastatic lesions using standard institutional procedures. The goal is to obtain 2 to 4 core needle biopsies using an 18 gauge needle. If a fine needle aspiration is performed, 3-6 passes should be obtained. Less than the goal amount of tissue is acceptable, and should be based upon the clinical judgment of the

Investigator and the clinician performing the procedure. The study coordinator will be present at the time of the biopsy to collect and process the tissue samples. Samples will be delivered to the laboratory of [REDACTED]. Specific processing and delivery instructions will be provided to all sites in the Laboratory Manual, which contains all details for specimen processing and handling.

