15.0 Reporting Adverse Drug Reactions

15.1 Adverse Event Definitions

Adverse Event

An adverse event (also known as an adverse experience) is defined as any untoward medical occurrence associated with the use of a drug in humans, whether or not considered drug related. More specifically, an adverse event (can be any unfavorable and unintended sign (e.g., an abnormal laboratory finding), symptom, or disease temporally associated with the use of a drug, without any judgment about causality. An adverse event can arise from any use of the drug (e.g., off-label use, use in combination with another drug) and from any route of administration, formulation, or dose, including an overdose.

Adverse reaction

An adverse reaction is defined as any adverse event caused by the use of a drug. Adverse reactions are a subset of all suspected adverse reactions for which there is reason to conclude that the drug caused the event.

Suspected

A suspected adverse reaction is defined as any adverse event for which there is a reasonable possibility that the drug caused the adverse event. For the purposes of IND safety reporting, “reasonable possibility” indicates that there is evidence to suggest a causal relationship between the drug and the adverse event. A suspected adverse reaction implies a lesser degree of certainty about causality than an adverse reaction.

Unexpected

An adverse event or suspected adverse reaction is considered *unexpected* if it is not listed in the investigator brochure or package insert(s), or is not listed at the specificity or severity that has been observed, or, if an investigator brochure is not required or available, is not consistent with the risk information described in the general investigational plan or elsewhere in the current application.

“Unexpected,” as used in this definition, also refers to adverse events or suspected adverse reactions that are mentioned in the investigator brochure as occurring with a class of drugs or as anticipated from the pharmacological properties of the drug, but are not specifically mentioned as occurring with the particular drug under investigation.

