15.5 Expedited Reporting

Participating Sites Reporting to Sponsor-Investigator (UCSF)

In addition to complying with all applicable regulatory reporting laws and regulations, each site will report the following information in writing to the Sponsor-Investigator within one business day of the Investigator’s awareness of occurrence:

- All SAEs
- Reports of pregnancy exposure (pregnancy encompasses the entire course of pregnancy and delivery, perinatal and neonatal outcomes, even if there were no abnormal findings; both maternal and paternal exposure is collected);
- Reports of lactation exposure;
- Overdose (with or without an SAE);
- Abuse (use for non-clinical reasons with or without an SAE);
- Inadvertent or accidental exposure; and
- Follow-up information regarding any of the above.
- The participating investigator should include his or her assessment of the causal relationship between each SAE and the Grantor product.

Reports will include the cover page provided, and reference the Protocol Number.

A copy of the report should be sent to the coordinating center CRC at UCSF. Information will be provided.

Sponsor-Investigator Reporting to the Data and Safety Monitoring Committee

If a death occurs during the treatment phase of the study or within 30 days after the last administration of the study drug(s) and it is determined to be related either to the study drug(s) or to a study procedure, the Investigator or his/her designee must notify the DSMC Chair (or qualified alternate) within 1 business day of knowledge of the event. The contact may be by phone or e-mail.

Sponsor-Investigator Reporting to UCSF Committee on Human Research (Institutional Review Board)

The Sponsor-Investigator must report events meeting the UCSF CHR definition of “Unanticipated Problem” (UP) within 5 business days of his/her awareness of the event.

Sponsor-Investigator Expedited Reporting to the Food and Drug Administration

The Sponsor-Investigator is responsible for determining whether or not the suspected adverse reaction meets the criteria for expedited reporting in accordance with Federal Regulations (21 CFR §312.32).

The Sponsor-Investigator must report in an IND safety report any suspected adverse reaction that is both serious and unexpected. The Sponsor-Investigator needs to ensure that the event meets all three definitions:

- Suspected adverse reaction (as defined in 6.1.30)
- Unexpected (as defined in 0)
- Serious (as defined in 6.1.5)

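### Serious complications of the required baseline biopsy, or of holding coumadin for it, fall outside the reportable-SAE window if they occur before the first PLX3397 dose

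*Combined protocol and SAP*

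**What the plan says.** **Reporting window.** Section 15.3: "Reportable SAEs are those that occur after the first dose of PLX3397"; the window closes 21 days after combined therapy ends. Section 9.1 starts safety evaluation at the same moment: "All patients will be evaluable for toxicity from the time of their first treatment with PLX3397".

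**Biopsy.** Section 14.1 places it "before treatment start in all eligible patients", for accessible tumor; lung-only disease is exempt. Section 8.1 and Table 8-2 list it among screening procedures. Section 3.1.2 puts the first phase II biopsy before PLX3397 starts and the second after the five-day lead-in.

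**Anticoagulation.** Section 3.2 admits patients on stable coumadin, "providing that anticoagulation can be safely held to an INR within normal range for the purpose of tumor biopsy".

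**Definition and attribution.** Section 15.1 defines an adverse event as "any untoward medical occurrence associated with the use of a drug in humans, whether or not considered drug related". Section 15.2: "The Investigator will assign attribution of the possible association of the event with use of the investigational drug". The table beneath that sentence also uses the broader word intervention.

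**Deaths.** Sections 15.5 and 16.3 send a death to the DSMC Chair within one business day. Section 15.5 applies this when "it is determined to be related either to the study drug(s) or to a study procedure", and 16.3 is similar. Both limit it to the treatment phase or 30 days after the last study drug.

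**The concern.** The biopsy serves the correlative aims, and the protocol itself recognises its risk: Section 3.2 sets coagulation limits before an initial visceral biopsy, and Section 3.3 excludes coagulopathy that precludes one. Yet the only sentence that defines a reporting window opens it after this procedure is done. A patient admitted with bleeding after the baseline biopsy, or with a clot while coumadin is held, has no SAE that Section 15.3 makes reportable if the event precedes her first dose. If she never starts PLX3397, she is not evaluable for toxicity under Section 9.1 either. Registration follows the completed pretreatment evaluation (Section 17.8), so she may appear only in the site's log of ineligible patients (Section 4.3.1).

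At stake is whether the sponsor and the DSMC reliably learn of serious harm from the first risk that the protocol imposes, and whether the published safety account includes it.

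**Working it through.** The plan states no figure on this point, so the main check sets the text in order of time and asks which rule reaches each event.

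**1. Which events fall outside the Section 15.3 window**

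| Event | Timing | Inside the window? |
|---|---|---|
| Complication of baseline biopsy or coumadin hold, before first PLX3397 dose | Screening | No |
| Same cause, onset after first dose | On treatment | Yes |
| Complication of second phase II biopsy | After lead-in | Yes |

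Only the first row is a gap. Table 8-2 places the baseline biopsy within the two weeks before entry, so the interval is short but real.

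**2. Whether another rule closes the gap**

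- *OnCore recording (15.2, 16.3).* All grade 3 or higher events in phase II, whatever the attribution, with no start date. This may capture the event. But the term recorded is an adverse event, which 15.1 ties to use of a drug, and no study drug has yet been used.
- *Site to sponsor-investigator (15.5).* All SAEs within one business day, with no start date. The same definition applies, and the causality assessment requested concerns the supplied product.
- *Sponsor-investigator to manufacturer (15.5).* Restricted to the SAE reporting period, and so tied to 15.3.
- *DSMC (16.1, 16.3).* Apart from cohort data, its remit is serious suspected adverse reactions, which 15.1 defines by a reasonable possibility that the drug was the cause. A biopsy bleed does not fit.
- *Procedure-related death rule (15.5, 16.3).* Starts with the treatment phase; a death before dosing is not clearly reached.
- *Unanticipated Problems to the IRB (15.5).* Not tied to dosing. May capture some events; the definition is not given.

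So some routes may catch an event before dosing, none clearly requires it, and two (manufacturer and DSMC) are worded so that it does not fit.

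**3. Scale**

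Inputs: n = 56, the phase II enrolment target (Sections 5.1, 12.3). This is an upper bound among enrolled patients, because lung-only and inaccessible disease is exempt. The complication rate p is an assumption. For simplicity, every complication is taken to occur before the first dose.

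Expected events = n × p. Chance of at least one = 1 − (1 − p)^n.

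| p (assumed) | Expected | At least one |
|---|---|---|
| 0.5% | 56 × 0.005 = 0.28 | 1 − 0.995^56 = 0.245 (24%) |
| 1% | 56 × 0.01 = 0.56 | 1 − 0.99^56 = 0.430 (43%) |
| 2% | 56 × 0.02 = 1.12 | 1 − 0.98^56 = 0.677 (68%) |

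If only half of the patients had a biopsy (28), the outer values fall to 1 − 0.995^28 = 13% and 1 − 0.98^28 = 43%.

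**4. Effect on the stopping guideline**

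Section 12.1 sets its 15% ceiling on treatment-related SAEs. A biopsy complication before dosing is not treatment-related, so it would not enter that count even if collection began earlier. No efficacy rule or sample size changes.

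**The case against.** A reader might infer that these complications are never reported or counted, so that the number reported is zero. The documents do not support that. The recording rule and the site rule on SAEs have no start date. A hospital admission would ordinarily meet the grade 3 description in Section 15.2, serious events in OnCore are reviewed every six weeks by the manufacturer or CRO (Section 15.4), and the IRB route is independent of dosing. A conscientious site could well report the event. The text is inconsistent; it is not a total exclusion.

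A reader might also see a contradiction between 15.3 and the death rule in 15.5 and 16.3. There is none on the wording. The death rule starts with treatment, and its reference to study procedures has a natural use for the second biopsy. It shows only that the plan regards procedure harm as something the DSMC should hear about.

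Other fair points stand. The coumadin condition concerns only patients taking it, and LMWH is preferred. Coagulation is checked before visceral biopsies. Some tissue will be taken during clinical procedures. With about one expected event at most over the assumed range, across three sites, no reporting rule would let the DSMC detect an excess by site or organ. The benefit is that each event is seen and assessed.

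What does not stand is that these routes make 15.3 harmless. A specific window and a drug-linked definition give a site good textual grounds not to report.

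**Conclusion.** The concern holds in a limited form. Serious complications of the baseline biopsy, or of a coumadin hold for it, that occur before the first PLX3397 dose are outside the reportable-SAE window and the toxicity-evaluable period. The remaining routes are inconsistent about them, and the DSMC has no clear route to them. Events after the first dose and events from the second phase II biopsy are covered.

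The size is small in absolute terms: 0.28 to 1.12 expected events and a 24% to 68% chance of at least one. This rests on an assumed rate of 0.5% to 2% and at most 56 enrolled patients with a biopsy. Patients who had a biopsy and then were not enrolled would add to this by a number that the documents do not give.

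The point bears on safety oversight and reporting. It leaves the primary endpoint, the sample size and the 15% stopping count untouched. It should be corrected because the gap is plain in the text and cheap to close.

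**What to change.** - **15.3:** make SAEs related to a protocol-required procedure, including anticoagulation held for it, reportable from consent. All other SAEs stay reportable from the first PLX3397 dose.
- **9.1, 15.1, 15.2, 15.5, 16.3:** reconcile the evaluability statement, the adverse event definition, the recording rules and the DSMC's remit with that window, and give each rule a start date.
- **15.2:** add a separate attribution for relation to a study procedure.
- **15.5 and 16.3:** start the rule on procedure-related deaths at consent.
- **Analysis (12.2):** tabulate procedure-related SAEs for all patients who had a biopsy, whether or not they were treated, apart from the 15% treatment-related stopping count.

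The cost is amendment wording, one CRF field and a few more SAE forms. The reported safety profile may look slightly less favourable. The change sets no dose and no rule on how biopsy or anticoagulation is managed.

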15.4 Adverse Events Monitoring

The Investigator will assess all adverse events and determine reportability requirements to the UCSF Data and Safety Monitoring Committee (DSMC); UCSF's Institutional Review Board, the Committee on Human Research (CHR); and to the Food and Drug Administration (FDA) if it meets the FDA reporting criteria.

Adverse events entered into OnCore® will be reviewed by the Helen Diller Family Comprehensive Cancer Center Site Committee on a weekly basis during Phase Ib and on a monthly basis during Phase II. The Site Committee will review and discuss at each meeting the selected toxicity, the toxicity grade, and the attribution of relationship of the adverse event to the administration of the study drug(s).

In addition, all adverse events and suspected adverse reactions considered “serious,” entered into OnCore® will be reviewed and monitored by the Plexxikon or the designated CRO every six (6) weeks, and prior to dose escalation. At the time of dose escalation, a written report will be submitted to the DSMC Chair (or qualified alternate) describing the cohorts, dose levels, adverse events, safety reports, and any Dose Limiting Toxicities observed, in accordance with the protocol. The report will be reviewed by the DSMC Chair (or qualified alternate). Approval for the dose escalation by the DSMC must be obtained prior to implementation. For a detailed description of the Data and Safety Monitoring Plan please see section 16.

